### Sample size calculations

**Specific Aim #1:** The number of subjects necessary to find statistical differences between our insulin resistant (**IR**) and our non-insulin resistant (**NIR**) groups in major endpoints of this study was calculated based on mean and standard deviation values derived from our preliminary studies and our previous publications (18, 24). The sample size calculations (Table 2) indicate that at least 17 subjects will be required for each group in this study. Our primary comparisons will be between the **IR** and **NIR** groups, but subjects will also be stratified into the **MIR** ("mildly insulin resistant") group. Based on previous work (27), we anticipate that our subjects will be stratified relatively evenly into our three study groups (i.e., **NIR**, **MIR**, and **IR**), but it is quite possible this may not be the case. Therefore, we plan to enroll a total of 60 subjects into this study in order to end with at least 17 subjects in both the **IR** and **NIR** groups.

Table 2. Sample size calculations for Specific Aim #1

	Power	$\alpha$	Expected $\Delta$ (%)	Estimated SD (%)	# of subjects
Fatty acid Ra	0.8	0.05	35%	30%	13
Adipogenic capacity assays	0.8	0.05	20%	20%	17
Adipocyte cell size	0.8	0.05	25%	25%	17

**Specific Aim #2:** The number of subjects necessary to find statistical differences between **IR** and **NIR** groups in key endpoints of the studies designed to address Specific Aim #2 was calculated based on mean and standard deviation values derived from our preliminary studies, work published in our previous publications (15, 16) and from previous work (14). For Specific Aim #2, we will only perform the analyses on samples from subjects in the **IR** and **NIR** groups. The sample size calculations (Table 3) indicate that we will need at least 17 subjects in both groups. For our proteomic analyses, we will use the samples collected from the number of subjects required for our targeted analyses to be statistically significant.

Table 3. Sample size calculations for Specific Aim #2

	Power	$\alpha$	Expected $\Delta$ (%)	Estimated SD (%)	# of subjects
Macrophage infiltration	0.8	0.05	20%	20%	17
Cytokine abundance	0.8	0.05	50%	40%	12
Muscle ceramide concentration	0.8	0.05	20%	20%	17

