### **Subject stratification**

As noted above, subjects will be stratified into 3 groups based on their degree of insulin resistance, as defined by their glucose disposal rate (GDR) measured via hyperinsulinemic/euglycemic clamp during the experiment.

- 1) ***“Insulin resistant” [IR]*** (GDR  $< 28 \mu\text{mol/kg fat free mass [FFM]/min}$ ),
- 2) ***“Mildly insulin resistant” [MIR]*** (GDR  $> 28 \mu\text{mol/kg FFM/min}$  and  $< 40 \mu\text{mol/kg FFM/min}$ )
- 3) ***“Non-insulin resistant” [NIR]*** (GDR  $> 40 \mu\text{mol/kg FFM/min}$ ).

The “cutoff points” used to stratify our subjects into these 3 groups were defined by Stern et al., (25). Stern, et al., used a statistical approach using hyperinsulinemic-euglycemic clamp data from 2,138 ethnically diverse non-diabetic subjects (insulin infusion rate =  $40 \text{ mU/m}^2/\text{min}$ , which is the same as we propose here). They defined the “optimal insulin resistance cutoff” as being  $< 28 \mu\text{mol/kg FFM/min}$ . We will make every effort to closely balance subject characteristics across the three study groups (including sex).

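### Does enrolling 60 subjects leave the two compared groups at real risk of falling short of 17 each?

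*Combined protocol and SAP*

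**What the plan says.** The Sample size calculations section derives a per-group number for the IR versus NIR comparison. For Specific Aim #1, "at least 17 subjects will be required for each group in this study"; for Specific Aim #2, the tables "indicate that we will need at least 17 subjects in both groups". On the three-way split it says "we anticipate that our subjects will be stratified relatively evenly into our three study groups", adds "but it is quite possible this may not be the case", and then draws the total from that: "we plan to enroll a total of 60 subjects into this study in order to end with at least 17 subjects in both", where the pair meant is IR and NIR.

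Under Subject stratification, subjects are grouped by degree of insulin resistance, "as defined by their glucose disposal rate (GDR) measured via hyperinsulinemic/euglycemic clamp during the experiment". The effort at balance promised there concerns subject characteristics, including sex, and not the number in each group.

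The Subjects section expects about half of those who consent not to take part, so 120 consents give 60 participants. The documents give no loss rate after that point, no probability of reaching 17 in both groups, and no rule to continue recruiting until both groups reach 17.

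**The concern.** The per-group number is calculated, but the step from 17 per group to 60 in total is not. Group is known only after the clamp, so nobody can be enrolled by group. The total exceeds 3 × 17 = 51 by 9, and the plan does not show how much protection that margin gives. On the plan's own premise of a roughly even split, the stated minimum is missed about one time in three.

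The primary comparison is IR versus NIR, and Aim 2 uses only those two groups, so mildly insulin resistant (MIR) subjects cannot make up a shortfall. If missing 17 in a group meant losing the planned 80% power, the justification for the total would be weak in both aims.

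**Working it through.** **Inputs from the documents.** Total 60; minimum 17 in IR and in NIR; Student's t-test; α = 0.05; power 0.8; differences and SDs from Tables 2 and 3. The row "Adipogenic capacity assays 0.8 0.05 20% 20% 17" is one of four with difference equal to SD (standardised effect d = 1.0).

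**Assumptions.** Two-sided test (not stated, but it reproduces the tables). One-third probability per group as the reading of a relatively even split. All other shares and all loss rates are illustrative.

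**1. Reproduce the plan's figure.** For a two-sided t-test with n per group, the noncentrality is d·√(n/2) on 2n − 2 degrees of freedom. Solving for 80% power:

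- d = 20/20 = 25/25 = 1.0: n = 16.71, so 17 (power at 17 is 0.807)
- d = 35/30 = 1.167: n = 12.57, so 13
- d = 50/40 = 1.25: n = 11.09, so 12

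All six rows of Tables 2 and 3 reproduce. A one-sided normal approximation gives 13 for the 17 rows and does not fit.

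**2. Chance of 17 in both groups.** With N = 60 and shares p₁ (IR), p₂ (NIR) and p₃ = 1 − p₁ − p₂ (MIR),

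P = Σ over i ≥ 17, j ≥ 17, i + j ≤ 60 of [60! / (i! j! (60 − i − j)!)] · p₁^i · p₂^j · p₃^(60 − i − j).

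At p₁ = p₂ = 1/3 this gives 0.6675 (0.6678 in one million simulated draws). One group alone reaches 17 with probability 0.831.

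**3. What a miss costs.** For unequal groups the noncentrality is d·√(n₁n₂/(n₁ + n₂)) on n₁ + n₂ − 2 degrees of freedom. At d = 1.0:

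| IR / NIR (either order) | Power |
|---|---|
| 17 / 17 | 0.807 |
| 16 / 18 | 0.806 |
| 15 / 20 | 0.811 |
| 16 / 17 | 0.794 |

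A group of 15 or 16 misses the target, but power barely moves when the other group is larger.

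**4. Power averaged over the random sizes.** Weighting the power at each (n₁, n₂) by its trinomial probability, at d = 1.0:

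| Shares IR/NIR, evaluable N | P(both ≥ 17) | Mean power | P(power < 0.80) |
|---|---|---|---|
| 1/3, 1/3; 60 | 0.67 | 0.86 | 7.5% |
| 35/35%; 60 | 0.78 | 0.87 | 2.7% |
| 40/30%; 60 | 0.64 | 0.87 | 5.3% |
| 50/25%; 60 | 0.32 | 0.86 | 12% |
| 40/25%; 60 | 0.30 | 0.83 | 26% |
| 50/20%; 60 | 0.08 | 0.795 | 44% |
| 40/20%; 60 | 0.07 | 0.76 | 64% |
| 35/20%; 60 | 0.05 | 0.74 | 78% |
| 1/3, 1/3; 57 (5% lost) | 0.53 | 0.84 | 16% |
| 1/3, 1/3; 54 (10% lost) | 0.38 | 0.82 | 31% |

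At thirds with 60, power falls below 0.75 with probability 1.2%. The 50/25 row shows how poorly the 17-and-17 criterion tracks power: its chance is less than half that at thirds, yet mean power is the same.

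**5. The two less demanding rows.** At thirds with 60, fatty acid Ra reaches its 13 per group with probability 0.97 (mean power 0.94), and cytokine abundance reaches its 12 with probability 0.98 (mean power 0.96).

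**The case for a change.** The best case for a change is that the plan names 17 as a minimum in both aims, concedes that an uneven split is quite possible, and then offers 60 as the remedy without showing how well it works. A reader cannot tell that the minimum is missed a third of the time on an even split, or that the outcome depends on the NIR share. With NIR at 20% and IR at 40%, mean power is 0.76 and is below 0.80 in 64% of splits. The 50% loss in the Subjects section falls between consent and participation, so it does not cover failed clamps or unusable samples among the 60. A sentence giving the odds would cost almost nothing.

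The facts in this stand: the probability is absent, there is no rule for continuing recruitment, and power does erode if the NIR group is small. Even with thirds and no losses, a 7.5% risk of power below 0.80 remains.

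The inference to a needed change does not stand. The documents give no share of 40/20 and no 5% or 10% loss, so the serious shortfalls come from assumptions brought to the plan. Testing is essentially a single clamp day, with imaging possibly on another occasion, which limits dropout among participants. The proposed sentence would leave enrolment, procedures and analyses as they are.

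**Conclusion.** No change is needed. The plan contains no arithmetic error: the per-group numbers reproduce, and no calculation from 17 to 60 is presented that could be wrong. The 60 is an aim with a margin of 9 over 51, set in answer to an uneven split that the plan itself anticipates.

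The 67% chance of 17 in both groups is correct under the one-third reading with no losses, but it measures a proxy. On that same premise the planned 80% power is kept in about 92% of splits and averages 0.86 at a standardised effect of 1.0. Assumed losses of 5% or 10% at thirds still leave mean power at 0.84 or 0.82. Of the cases examined, mean power falls below 0.80 only where the NIR share is 20%.

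What remains is an unstated planning probability. The realised group sizes will be known as soon as the clamps are done, and the precision of the IR versus NIR comparison can then be judged from them directly.

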## **RESEARCH DESIGN AND METHODS**

### **Overall strategy**

- We will recruit a cohort of abdominally obese adults who will be very similar in terms of body mass index (BMI), fat mass, fat free mass, waist circumference, and habitual physical activity behavior (sedentary).
- We will measure insulin sensitivity (hyperinsulinemic-euglycemic clamp) and then stratify the subjects into 3 groups based on their degree of insulin resistance. 1) "***Insulin resistant***" [**IR**], 2) "***Mildly insulin resistant***" [**MIR**], and 3) "***Non-insulin resistant***" [**NIR**]. The "cutoff points" used for stratifying our subjects into these 3 groups were defined by Stern et al., (25).
- We will also measure systemic fatty acid kinetics (stable-isotope dilution methods) and we will collect subcutaneous adipose tissue biopsy samples.
- In these adipose tissue samples, we will perform extensive, yet very relevant and integrated analyses of factors regulating fatty acid storage and mobilization, adipogenesis, fat cell size, capillarization, angiogenesis, and fibrosis.
- We will also collect skeletal muscle biopsy samples to assess factors in muscle that may also be different in insulin resistant [**IR**] and non-insulin resistant [**NIR**] obese adults.
- Several other important phenotypic measures will be performed to help characterize the subjects (e.g., subcutaneous and visceral adiposity [MRI analysis], hepatic lipid accumulation and degree of hepatic fibrosis [MRI analysis], basal metabolic rate, blood lipid profile)
- Our primary comparisons to assess factors contributing to protection against insulin resistance will be performed on the most-insulin resistant [**IR**] and least-insulin resistant [**NIR**] groups, but we will also perform correlational analyses using the entire subject population.

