### **Primary phenotype measurements for Specific Aim #1**

During the clinical study outlined above, we will perform several clinical and sub-clinical assessments to help characterize our subject population.

**Insulin resistance** will be assessed during the hyperinsulinemic-euglycemic clamp. The primary measure of insulin resistance will be calculated as the steady-state rate of glucose infusion (GDR) during the 20 min period at the end of the clamp. We will also assess hepatic insulin resistance (i.e., magnitude of reduction in hepatic glucose production (HGP) in response to insulin) using stable isotope tracer methods, and peripheral tissue insulin resistance (i.e., difference between whole-body GDR and HGP). Detailed methods for this procedure, including methods used to quantify the tracer-tracee ratio (TTR) for  $d_2$ -glucose using gas chromatography/mass spectrometry (GC/MS) can be found in our recent publication (16).

**In vivo rates of lipolysis and fatty acid mobilization in the systemic circulation** We will measure TTR for  $d_5$ -glycerol and  $^{13}\text{C}$ -palmitate using the same GC/MS analysis methods we have used previously in many of our studies (4, 17, 21, 22, 26).

**Resting energy expenditure and fat oxidation rate** will be measured using indirect calorimetry (7).

**Plasma substrates and hormone concentrations**. Plasma concentrations of triglyceride, fatty acid, glucose and insulin will be assessed using commercially available assays kits (Sigma, Wako, and ThermoDMA, Millipore, respectively). Plasma epinephrine and norepinephrine will be measured by HPLC with electrochemical detection by the pathology lab at the University of Michigan Medical Center.

**Blood lipid profile**. Plasma concentrations of total- and high-density lipoprotein cholesterol (Total-C and HDL-C) will be measured using commercially available colorimetric assay kits; Cholesterol E and HDL-Cholesterol E; WAKO Life Sciences, Inc.) and plasma low-density lipoprotein (LDL) cholesterol will be calculated as:  $[\text{LDL-C}] = [\text{Total-C}] - [\text{HDL-C}] - [\text{Triglyceride}]/5$ .

**Body composition and visceral adiposity**. Percent body fat will be assessed using a Dual Energy X-ray Absorptiometry [DEXA: Lunar DPX, DEXA Scanner]. We also plan to measure hepatic fibrosis, the amount of fat stored in the liver and visceral fat (or intra-abdominal fat) using magnetic resonance imager (MRI) with elastography as described previously (1).

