### Statistical analysis

Student's t-test will be used to assess statistical significance of our major endpoints between **NIR** and **IR**. In addition, we will perform linear regression analyses using our entire cohort of subjects (**NIR**, **MIR**, and **IR**) to assess relationships between each of our major endpoints and insulin resistance. Finally, we will also conduct multiple regression analysis using our entire cohort to assess the relative contribution of each of our major endpoints to the variance of insulin resistance. A *P* value of  $\leq 0.05$  will be considered statistically significant.

For our untargeted analyses, the false discovery rate (FDR) for both proteins and peptides will be set to 0.01. In addition, only phosphosites with a localization probability greater than 0.75 will be considered as "identified", a threshold used commonly in phosphoproteome studies. To be used in comparisons between groups, phosphorylation sites need to satisfy the following criteria: 1) identified in more than half of the samples; and 2) with a fold change (or difference) greater than 1.5 between comparisons. For comparisons between groups for both our untargeted and target endpoints, a Student's t-test will be used to assess statistical significance of our major endpoints for our primary comparison between the **NIR** and **IR** groups. In addition, we will perform simple linear regression analyses to assess relationships between each of our major endpoints and insulin resistance. Finally, we will also conduct multiple regression analysis to assess the relative contribution of each of our major endpoint measures to the variance of insulin resistance. A *P* value of  $\leq 0.05$  will be considered statistically significant.

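### Whole-cohort regressions are planned, but Aim 2 samples are analysed only in IR and NIR; R-squared from the two extreme groups is inflated and not comparable with whole-cohort values

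*Combined protocol and SAP*

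**What the plan says.** Three places bear on which subjects enter the regressions.

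- **Overall strategy.** The primary comparison is IR against NIR, but "we will also perform correlational analyses using the entire subject population".
- **Statistical analysis, first paragraph.** "we will perform linear regression analyses using our entire cohort of subjects", with NIR, MIR and IR all named, and then "multiple regression analysis using our entire cohort to assess the relative contribution of each of our major endpoints to the variance of insulin resistance". Neither sentence is limited to Aim 1.
- **Sample size calculations, Specific Aim #2.** "For Specific Aim #2, we will only perform the analyses on samples from subjects in the" IR and NIR groups.

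The second paragraph of Statistical analysis, which opens with the untargeted analyses, repeats both models: "we will perform simple linear regression analyses to assess relationships between each of our major endpoints and insulin resistance" and "multiple regression analysis to assess the relative contribution of each of our major endpoint measures to the variance of insulin resistance". It names NIR and IR for the t-test but gives no cohort for the regressions.

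Subject stratification forms the groups by cutting GDR at 28 and 40 µmol/kg FFM/min. Primary phenotype measurements makes the same GDR the primary measure of insulin resistance.

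**The concern.** A whole-cohort regression on an Aim 2 tissue endpoint cannot be run if MIR samples are not analysed. For Aim 2 the plan is therefore partly contradictory and partly silent.

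The statistical problem is that GDR both defines the groups and is the outcome whose variance the multiple regression is meant to explain. Dropping the MIR band selects subjects on the outcome. It widens the GDR variance and so raises correlations, R-squared and any slope with GDR as the dependent variable. Aim 1 figures would describe the whole cohort and Aim 2 tissue figures only its two ends, although both would be described as contributions to the variance of insulin resistance.

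A multiple regression that mixes Aim 1 and Aim 2 tissue endpoints, if fitted to complete cases, would also lose the MIR subjects: about 20 of 60 under an even split. It might still be reported as an entire-cohort model.

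**Working it through.** **1. The plan's own figures.** A two-sided two-sample t-test at alpha 0.05 and power 0.80 (noncentral t) gives 17, 12 and 17 per group for Table 3 and 13, 17 and 17 for Table 2, exactly as printed. The sample sizes are not in question.

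**2. Inputs.** From Table 3, the standardised difference d between IR and NIR is 20/20 = 1.0 for macrophage infiltration and muscle ceramide, and 50/40 = 1.25 for cytokine abundance. The plan enrols 60 subjects and expects a roughly even split, while saying this is not assured. It gives no GDR distribution. I assume normal GDR, a linear relation and constant residual variance. With cutoffs at 28 and 40, a normal even split implies mean 34 and SD 6/0.431 = 13.9.

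**3. GDR variance in the extremes.** In SD units the cut is at c = 0.431, with normal density φ(c) = 0.364. The variance ratio, extremes to whole cohort, is

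u² = 1 + c·φ(c)/(1/3) = 1.470.

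**4. Whole-cohort R² implied by d.** The outer-third means differ by D = 2·φ(c)/(1/3) = 2.18 SD. The GDR variance within an outer third is w = 1.470 − (2.18/2)² = 0.28. Setting d² = R²D²/(1 − R²(1 − w)) gives R² = d²/(D² + d²(1 − w)):

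- d = 1.0: 1/(4.76 + 0.72) = 0.183
- d = 1.25: 1.5625/(4.76 + 1.125) = 0.266

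**5. Extreme-group R².** R²ₑ = R²u²/(1 + R²(u² − 1)):

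| d | Whole cohort | IR + NIR | Relative rise |
|---|---|---|---|
| 1.0 | 0.183 | 0.247 | +35% |
| 1.25 | 0.266 | 0.347 | +31% |

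**6. Sensitivity to the split (normal GDR).**

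| IR/NIR share, % | d = 1.0 | d = 1.25 |
|---|---|---|
| 28.3/28.3 (17 of 60 each, the plan's floor) | +52% | +46% |
| 30/30 | +46% | +40% |
| 35/35 | +31% | +26% |
| 40/40 | +18% | +15% |
| 40/25 | +36% | +31% |
| 50/30 | +17% | +14% |

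With an even split and uniform, lognormal, gamma or bimodal GDR, the rise is 27% to 35%.

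**7. Multiple regression.** With the three Table 3 endpoints together and an assumed residual correlation between them of 0 to 0.7, total R² goes from 0.447 to 0.543 (at 0) and from 0.269 to 0.352 (at 0.7), a rise of 22% to 30%.

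**8. Simulation.** 20,000 cohorts of 60, split 20/20/20, d = 1.0, slopes per SD:

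| Quantity | All 60 | 40 extremes |
|---|---|---|
| Adjusted R² | 0.177 | 0.238 |
| Slope of GDR on endpoint | 0.426 | 0.580 |
| Slope of endpoint on GDR (SE) | 0.427 (0.120) | 0.427 (0.121) |
| Power | 0.935 | 0.925 |
| Type I error | 0.052 | 0.050 |

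For two endpoints of equal true strength, one analysed in all 60 and the other in the extremes, the extreme-group R² is the larger in 68% of cohorts, against 50% without the bias. The SD of the difference is 0.14. For the same endpoint analysed both ways it is larger in about 99%. Correcting the extreme-group correlation with r/√(u² + r²(1 − u²)) returns an R² of 0.179.

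**The case against.** The two paragraphs of Statistical analysis can be read as one per aim. The second speaks of untargeted and targeted endpoints, which matches Hypotheses 2A and 2B, and it drops the entire-cohort wording both times. On that reading it agrees with the Aim 2 restriction, and only the general sentence in Overall strategy is out of line. This is a fair reading and it softens the contradiction. It does not remove the statistical problem, because it confirms that the Aim 2 regressions run on the extremes alone.

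Little of what is planned is damaged. The primary t-tests, error rate, power and endpoint-on-GDR slope stand. Relative shares within a single Aim 2 model barely move: 0.255/0.491/0.255 in the whole cohort against 0.261/0.478/0.261 in the extremes, at residual correlation 0.5. The plan does not name R-squared as a reported measure, does not fix the direction of the simple regressions, and announces neither a comparison across aims nor a mixed model. All of this stands, and it limits the weight of the point. But the stated target is contribution to the variance of insulin resistance, and the total variance explained is what the selection distorts.

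The size rests on assumptions that the documents cannot confirm, and for one pair of endpoints the bias (about 0.065) is under half the sampling SD of the difference (0.14). That is correct: it tilts a comparison and does not decide it. The direction was the same at every split and GDR shape examined.

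**Conclusion.** The concern holds. The sections disagree on, or leave open, the cohort for the Aim 2 regressions. Under the one explicit rule, the restriction to IR and NIR, R-squared and GDR-on-endpoint slopes for Aim 2 tissue endpoints are inflated by selection on the outcome.

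For the planned effects and an even split, the inflation is 6.5 points of R-squared (+35%) at d = 1.0 and 8.2 points (+31%) at d = 1.25. The range is 14% to 52% over the splits examined. These sizes are illustrative, since they assume linearity and a GDR distribution that the plan does not give.

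As a concrete case, adipogenic capacity (Table 2) and muscle ceramide (Table 3) have the same planned effect, yet their expected R-squared would be about 0.18 and 0.25 from sampling alone. The analyses are secondary and the primary comparison is sound, so this should be corrected but does not threaten the main result.

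**What to change.** Reconcile Overall strategy, Statistical analysis and Sample size calculations by naming the cohort for every regression. For Aim 2 tissue endpoints assayed only in IR and NIR:

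- Regress the endpoint on GDR, not the reverse.
- Label any r or R-squared as an extreme-group value, or range-correct it using the GDR variance of all 60 subjects.
- Do not compare it with Aim 1 values or present it as variance explained in the whole cohort.
- Keep the relative-contribution model within Aim 2 if wanted, with that label. Give the same label to any model mixing Aim 1 and Aim 2 tissue endpoints.

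Hepatic lipid (Hypothesis 2A, item d) is an MRI measure, not a tissue sample, and can be analysed in the whole cohort.

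The cost is wording and a small analysis step, with no extra subjects or assays and almost no loss of precision (slope SE 0.121 against 0.120). The downside is that no direct whole-cohort variance-explained figure is available for Aim 2 tissue endpoints, and a range-corrected one depends on linearity and constant residual variance. If the sponsor does want that figure directly, the MIR samples would have to be assayed, at additional laboratory cost. The change recommended here does not require this.
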